#### **Part A:**

The first key secondary estimand for this study is defined as follows:

- Target population: participants with EMAS-associated seizures who have not achieved adequate control from other ASMs.
- Endpoint: proportion of participants who achieve  $\geq 50\%$  reduction from baseline in EMAS-associated seizures over the 14-week treatment period.
- Measure of IMP effect: proportion of responders during the treatment period, regardless of any intercurrent events. This measure of effect follows a treatment policy strategy for handling intercurrent events.

The second key secondary estimand for this study is defined as follows:

- Target population: participants with EMAS-associated seizures who have not achieved adequate control from other ASMs.
- Endpoint: CGIC score at Week 14.
- Measure of IMP effect: CGIC score at Week 14, regardless of any intercurrent events. This measure of effect follows a treatment policy strategy for handling intercurrent events.

The third key secondary estimand for this study is defined as follows:

- Target population: participants with EMAS-associated seizures who have not achieved adequate control from other ASMs.
- Endpoint: change in total seizure frequency during the 14-week treatment period compared to baseline.
- Measure of IMP effect: change in total seizure frequency during the treatment period, regardless of any intercurrent events. This measure of effect follows a treatment policy strategy for handling intercurrent events.

For the first key secondary endpoint, a binary indicator for response (at least a 50% reduction from baseline in seizure frequency over the 14-week treatment period) equaling either 1 or 0, a single Bayesian hierarchical logistic regression model will be applied to the 4 populations (DS,

LGS, TSC, and EMAS). The model will take a form similar to the primary analysis model. Complete details will be provided in the ADR.

For CGIC, a Bayesian hierarchical ordinal logistic regression model will be applied to the 4 populations. This model will take a form similar to the primary analysis model and will be detailed in the ADR.

Change in total seizure frequency will be analyzed in the same way as the primary endpoint. Full details will be provided in the ADR.

#### **Part B:**

Key secondary endpoints for Part B (long term) will be descriptive, with no formal statistical inference, and will be summarized by treatment group over time, using appropriate summary statistics.

##### **9.4.3.2. Other Secondary Efficacy Endpoints**

- PGIC score
- Proportion of participants who achieve  $\geq 25\%$ ,  $\geq 75\%$ , and 100% reduction from baseline in EMAS-associated seizures
- Proportion of participants who achieve  $\geq 25\%$ ,  $\geq 50\%$ ,  $\geq 75\%$ , and 100% reduction from baseline in total seizures
- Change from baseline in number of EMAS-associated seizure-free days (Part A only)
- Time to baseline seizure frequency (Part A only)
- Proportion of participants with  $\geq 25\%$  and  $\geq 50\%$  reduction in the number of days per week with myoclonic seizures during the treatment period

Secondary endpoints will be summarized by treatment group over time using appropriate descriptive statistics for Part A and Part B.

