### 3. OBJECTIVES AND ENDPOINTS

#### 3.1. Part A

Primary	

To evaluate the efficacy of GWP42003-P compared with placebo in reducing the frequency of EMAS-associated seizures

	

Change in EMAS-associated seizure frequency (myoclonic-tonic, tonic, clonic, or tonic-clonic) during the 14-week treatment period compared to baseline

Key Secondary	

To evaluate the rate of treatment response to GWP42003-P compared with placebo in reducing the frequency of EMAS-associated seizures

	

Proportion of participants who achieve <math>\geq 50\%</math> reduction from baseline in EMAS-associated seizures over the 14-week treatment-period

To evaluate the effect of GWP42003-P compared with placebo on caregiver impression of change

	

CGIC score at Week 14

To evaluate the effect of GWP42003-P in reducing the frequency of all seizure types compared with placebo

	

Change in total seizure frequency during the 14-week treatment period compared to baseline

Secondary	

To evaluate the effect of GWP42003-P compared with placebo on physician impression of change

	

PGIC score at Week 14

To evaluate the effect of GWP42003-P compared with placebo on additional antiepileptic measures from daily seizure diaries

	

Proportion of participants who achieve <math>\geq 25\%</math>, <math>\geq 75\%</math>, and 100% reduction from baseline in EMAS-associated seizures over the 14-week treatment period

Proportion of participants who achieve <math>\geq 25\%</math>, <math>\geq 50\%</math>, <math>\geq 75\%</math>, and 100% reduction from baseline in total seizures over the 14-week treatment period

Change from baseline in number of EMAS-associated seizure-free days over the 14-week treatment period

Proportion of participants with <math>\geq 25\%</math> and <math>\geq 50\%</math> reduction in the number of days per week with myoclonic seizures during the treatment period

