#### Part A:

The duration of study participation is approximately 26 weeks, which includes a 1- to 3-week screening period, 4-week baseline observation period, 14-week dose-optimization treatment period, 10-day taper period, and a safety follow-up period (4 weeks after end of taper visit).

After the ICF has been signed, participants will be screened to enter the study from Day -49 to Day -35 (Visit 1) and commence a 28-day baseline period beginning at Day -28 (Visit 2), before returning for a randomization visit and treatment initiation (Day 1 [Visit 3]).

On Day -28 (Visit 2), participants who continue to meet eligibility criteria will be contacted by phone and commence a 28-day baseline period, before returning for a randomization visit and treatment initiation (Day 1 [Visit 3]).

On Day 1 (Visit 3), participants will be randomized centrally in a 1:1 ratio to receive either GWP42003-P or matching placebo. Randomization will be stratified by clobazam use (on/off) and age of seizure onset (3 years of age and younger or older than 3 years of age).

IMP administration during the 14-week treatment period will follow a flexible titration schedule to enable optimization of dosage:

- Participants will be initiated on a dose of 2.5 mg/kg BID (5 mg/kg/day) on Day 1 (Visit 3), and after 1 week, the dose will be increased to 5 mg/kg BID (10 mg/kg/day) at the Day 8 (Visit 4) phone visit.
- For participants who are tolerating the IMP at 5 mg/kg BID (10 mg/kg/day) and require further reduction of seizures, investigators may choose to increase their dosage up to a maximum dosage of 10 mg/kg BID (20 mg/kg/day). The decision to titrate above 5 mg/kg BID (10 mg/kg/day) should be based on the observed efficacy, safety, and tolerability of the participant (including review of laboratory values) per the clinical judgement of the investigator.

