#### 9.4.1. General Considerations

Unless stated otherwise, continuous data will be summarized using descriptive statistics comprising the number of participants with data to be summarized (n), mean, SD, median,

minimum (min), and maximum (max). Categorical variables will be summarized by the frequency and proportion of participants falling into each category.

For plasma concentration data and PK parameters, geometric mean, CV, and geometric CV will also be computed.

Unless stated otherwise, baseline is defined as the last record or measurement collected prior to the first dose of IMP on Day 1 (Part A Visit 3). Baseline for Part B is the same as the baseline for Part A.

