### **9.4.3. Secondary Endpoint(s)**

The following endpoints will be compared by treatment group over the treatment period:

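### The non-key Part A efficacy endpoints have placebo-comparative objectives but are given only by-arm descriptive summaries, and time to baseline seizure frequency is left undefined

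*Combined protocol and SAP*

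**What the plan says.** Section 3.1 (Part A) states two secondary efficacy objectives, both comparative: "To evaluate the effect of GWP42003-P compared with placebo on physician impression of change" and "To evaluate the effect of GWP42003-P compared with placebo on additional antiepileptic measures from daily seizure diaries". Section 9.4.3 introduces the secondary endpoints with "The following endpoints will be compared by treatment group over the treatment period".

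Section 9.4.3.2 lists the non-key efficacy endpoints: PGIC; responder levels for EMAS-associated and for total seizures; EMAS-associated seizure-free days; time to baseline seizure frequency; and responders on days per week with myoclonic seizures. One sentence covers their analysis: "Secondary endpoints will be summarized by treatment group over time using appropriate descriptive statistics for Part A and Part B".

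Section 9.4.1 gives the default content of a descriptive summary. For continuous variables, "continuous data will be summarized using descriptive statistics comprising the number of participants with data to be summarized (n), mean, SD, median", with minimum and maximum. For categorical ones, "Categorical variables will be summarized by the frequency and proportion of participants falling into each category".

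The time endpoint appears by name only, as "Time to baseline seizure frequency (Part A only)" in section 9.4.3.2 and without further definition in the synopsis and section 3.1.

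Section 9.4 describes itself as a summary, with fuller detail to come in the interim analysis SAP, the SAP and the ADR.

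**The concern.** A by-arm table of means or percentages is not an estimate of a treatment effect. For these endpoints the text promises a comparison, then specifies summaries that contain no difference, ratio or interval. The same rule serves randomized Part A and uncontrolled Part B, although only Part A has a placebo arm to compare with.

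What is at stake is the reading of the supportive evidence. The trial may stop accrual with about 30 children per arm, and percentages without intervals would then invite over-reading in either direction. An estimate chosen after the data are seen would also carry less weight than one named in advance.

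The time endpoint adds a separate problem. Some children may never have the event during treatment, and the text does not say how they are handled.

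**Working it through.** The documents give no sample size, power or event figure for these endpoints, so there is no plan figure to reproduce. The check is textual, with arithmetic for scale.

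**1. The sections side by side**

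- Objectives (3.1): comparative with placebo.
- Lead-in (9.4.3): compared by treatment group.
- Method for the key secondaries (9.4.3.1): a Bayesian hierarchical logistic model for the 50% responder endpoint, an ordinal logistic model for CGIC, and the primary-type analysis for total seizure frequency. All give between-arm effects.
- Method for the non-key endpoints (9.4.3.2): by-group descriptive summary only.
- Where no inference was intended, the protocol says so: 9.4.3.1 states it for the Part B key secondaries. No such statement covers the Part A non-key endpoints.
- The synopsis applies almost the same descriptive phrase to Part B alone. Summarizing over time also does not suit Part A PGIC, which by Table 1 has one post-baseline rating, at Visit 9; Visit 1 is only a memory aid.

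**2. Precision of an arm difference in proportions**

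Inputs: 60 per arm at the maximum of 120 (section 4.4), and 60/2 = 30 per arm if accrual stops at the first interim (section 9.5). The response rates are assumptions.

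Half-width = 1.96 × sqrt[p1(1 - p1)/n + p2(1 - p2)/n]

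| Assumed rates | n = 60 per arm | n = 30 per arm |
|---|---|---|
| 50% and 50% (widest case) | 17.9 points | 25.3 points |
| 45% and 25% | 16.7 points | 23.6 points |
| 10% and 2% | 8.4 points | 11.8 points |

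In the last row the expected number of responders at 2% is 0.02 × 60 = 1.2 or 0.02 × 30 = 0.6. An adjusted odds ratio may not be estimable there, and the Wald formula is only a guide.

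**3. Time to baseline seizure frequency**

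Inputs: baseline of 28 days (section 4.1: "commence a 28-day baseline period beginning at Day -28 (Visit 2)") and treatment of 14 × 7 = 98 days. Two assumptions are needed: the event is the day on which the treatment-period count reaches the 28-day baseline count, and the seizure rate under treatment is constant.

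For a proportional reduction r, time to event = 28/(1 - r) days:

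- r = 0.50: 28/0.50 = 56 days
- r = 0.70: 28/0.30 = 93 days
- r = 0.75: 28/0.25 = 112 days

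No event occurs by day 98 when r > 1 - 28/98 = 71.4%. If the baseline count covered 31 days, using the +3-day window on Visit 3, the threshold would be 1 - 31/98 = 68.4%. A constant 75% reduction lies outside even a treatment period lengthened by the Visit 9 window (98 + 7 = 105 days).

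**4. What would follow if children without an event were left out of the summary**

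This is an illustration on assumed inputs: Poisson counts; median baseline of 30 seizures per 28 days; median on-treatment rate ratio of 0.50 to 0.60 (active) and 0.80 to 0.85 (placebo); between-child SD of the log rate ratio of 0.6 to 0.8.

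- Children with no event: about 11% to 24% on active and 4% to 10% on placebo.
- Arm difference in median time, all children kept: 13 to 21 days.
- Arm difference in median time, observed times only: 8 to 15 days.
- Shrinkage across scenarios: from 1 - 10.4/13.4 = 22% to 1 - 11.7/20.5 = 43%.

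**The case against.** The strongest reply has four parts.

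**Section 9.4 is a summary and the SAP will say more.** This limits the point to the protocol text, because the separate SAP was not available. It does not remove the point: section 9.4 says the later documents will elaborate the analyses described there, and what is described for these endpoints is a descriptive summary. For the key secondaries the protocol names a model and then defers detail; here it names no comparative method to elaborate.

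**The wording conflict is loose drafting.** The 9.4.3 lead-in also covers Part B items and safety data, so comparison may mean presentation side by side. That is a fair reading of the lead-in, but it does not account for the comparative objectives in section 3.1.

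**Modelling the primary and key secondary endpoints and describing the rest is a defensible hierarchy.** It is, and no formal test is needed. A reader could also derive unadjusted differences and intervals from counts, means and SDs, so it would be too strong to say that the objectives cannot be answered. This does not help the time endpoint, and it leaves the choice of estimate open until after the data are seen.

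**A reader might infer that the plan drops its best responders and so biases the time endpoint against GWP42003-P.** The documents do not support that as a fact. They define no event and state no exclusion. The 9.4.1 list is a default that applies unless stated otherwise, and 9.4.3.2 asks for appropriate statistics, a term wide enough for Kaplan-Meier. What stands is that the event, the censoring rule and the summary are all unstated.

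**Conclusion.** The point holds for the non-key Part A efficacy endpoints in section 9.4.3.2, on the protocol text: the objectives are comparative and the stated analysis is not. It would be wrong to extend it to all Part A secondary endpoints, since the three key ones have between-arm models. Primary and key secondary inference is unaffected, so the severity is minor to moderate.

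The precision figures rest on assumed response rates. The 71.4% threshold depends on an assumed event definition and a constant seizure rate. The 22% to 43% shrinkage depends further on the illustrative inputs and on leaving out children without an event, which no section prescribes. These figures show why the time endpoint needs a definition and a censoring rule; they do not predict bias in this trial.

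**What to change.** For Part A, reconcile section 9.4.3 with 9.4.3.2 by replacing the single descriptive sentence. Report each endpoint with a between-arm estimate and a 95% interval labelled nominal, with no formal test:

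- **Responder endpoints:** risk difference, stratified by clobazam use and age at seizure onset where counts allow, otherwise unadjusted or exact.
- **PGIC:** ordinal odds ratio.
- **Seizure-free days:** adjusted mean difference.
- **Time to baseline seizure frequency:** state the event; use Kaplan-Meier by arm with censoring at the last treatment-period diary day, plus a hazard ratio with its interval.

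Keep descriptive statistics for Part B.

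The cost is wording and modest extra programming for about 12 analyses (1 PGIC, 3 + 4 responder levels, 1 seizure-free days, 1 time endpoint, 2 myoclonic-day levels). Because no test is added, there is no multiplicity cost. Intervals for sparse endpoints such as 100% response will be wide relative to any likely difference, and the report should say so.

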#### **9.4.5. Safety Analysis**

Safety data will be summarized using appropriate descriptive statistics.

##### **9.4.5.1. Treatment Compliance and Extent of Treatment Exposure**

Treatment compliance and exposure to treatment will be summarized.

##### **9.4.5.2. Adverse Events**

AEs will be coded according to the Medical Dictionary for Regulatory Activities dictionary.

A TEAE is one that started, or worsened in severity or seriousness, following the first dose of IMP.

Descriptive presentations of TEAEs will be produced by preferred term and System Organ Class for the safety analysis set. The number of participants reporting at least 1 AE will be provided.

The following summaries will be produced:

- All-causality AEs
- Treatment-related AEs
- All-causality AEs by severity
- All-causality serious AEs
- Serious AEs
- Treatment-related serious AEs
- AEs of special interest
- AEs reported as leading to permanent cessation of study treatment
- Fatal AEs

##### **9.4.5.3. Clinical Laboratory Data**

Clinical laboratory data at each visit, along with the change from baseline and percent change from baseline to each post-baseline visit will be summarized for the safety analysis set using appropriate summary statistics. Categorical shift tables will also be presented, showing the numbers of participants with values outside the normal range.

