### **2.3. Benefit/Risk Assessment**

Participants in the current study may experience some improvement of symptoms (beyond that of an assessment of their medical status) from participating in the study. Refer to [Section 2.2](#) for details regarding antiseizure efficacy observed in previous epilepsy clinical studies with GWP42003-P, including patients with EMAS from the EAP. The risks of participation are primarily those associated with adverse reactions to the IMP, although there may also be some discomfort from collection of blood samples and other study procedures. More information about the known and expected benefits, risks, and reasonably anticipated AEs associated with GWP42003-P may be found in the current approved version of the IB (GWP42003-P IB).

GWP42003-P is purified CBD, approved in the US as Epidiolex®, indicated for the treatment of seizures associated with LGS, DS, and TSC in patients 1 year of age and older and approved in the EU, indicated for the adjunctive treatment of seizures associated with LGS and DS, in conjunction with clobazam, in patients 2 years of age and older and for adjunctive treatment of seizures associated with TSC in patient 2 years of age and older. The most commonly reported side effects include somnolence; decreased appetite; diarrhea; transaminase elevations; fatigue, malaise, and asthenia; rash; insomnia, sleep disorder, and poor-quality sleep; infections; pyrexia; and vomiting. Serious side effects include hepatocellular injury, somnolence and sedation, suicidal behavior and ideation, hypersensitivity reactions, and withdrawal of ASMs. Further information is included in the latest GWP42003-P (Epidiolex) United States Prescribing Information and/or Summary of Product Characteristics.

Overall, based on the extensive clinical safety and efficacy results of GWP42003-P demonstrated across 5 Phase 3 studies, 2 open-label studies, and the EAP in the treatment of pediatric epilepsy syndromes, it is believed that GWP42003-P has a favorable benefit-risk profile for the treatment of EMAS.

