After Part B Week 14 (Visit 7), serum transaminases and total bilirubin levels should be evaluated within 1 month following changes in GWP42003-P dosage and in medications that are known to impact the liver.

- As much as possible, laboratory assessments should be done centrally via IQVIA Mobile Health Solutions (if done locally, laboratory results should be filed in source documents and any abnormal and clinically significant results should be recorded as AEs)

A safety follow-up visit (phone call) will be conducted 4 weeks after the end-of-taper visit. If a participant withdraws from the study prematurely (ie, before the end of treatment visit), an early withdrawal visit will be conducted, and a safety follow-up phone call will occur 4 weeks after their last dose of IMP. Participants who discontinue IMP prematurely should be encouraged to complete the end of treatment visit and taper period.

Unscheduled phone visits can occur at any time during Part B, as needed.

During Part B, eDiaries will be completed at least weekly. No food eDiary is required for Part B.

Schematics ([Figure 1](#) for Part A and [Figure 2](#) for Part B), presented in [Section 1.2](#), depicts the overall trial design. A detailed outline of procedures and activities is provided in the SoA

([Table 1](#) for Part A and [Table 2](#) for Part B). More detailed information on treatment and study procedures is provided in [Section 6](#) and [Section 8](#), respectively.

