### Medical Conditions

15. Has a history of psychogenic non-epileptic seizures that confounds the assessment of the primary efficacy measure.
16. Has clinically significant unstable medical condition(s), other than EMAS.
17. Has a clinically significant illness in the 28 days prior to screening (Part A Visit 1) or randomization (Part A Visit 3), other than epilepsy, which in the opinion of the investigator could affect seizure frequency.
18. Has presence of focal seizures or persistent focal epileptiform discharges on EEG.
19. Has a history of infantile spasms.
20. Has moderate to severe neurocognitive and/or developmental delay prior to seizure onset.
21. Has a progressive neurological condition.
22. Has known or suspected hypersensitivity to cannabinoids or any of the excipients of GWP42003-P such as sesame oil.
23. Is unwilling or unable to remain stable on concurrent ASMs throughout the study.
24. Has, in the opinion of the investigator, clinically significant abnormalities in the ECG measured at screening (Part A Visit 1), or any concurrent cardiovascular conditions, which will interfere with the ability to read their ECGs.
25. Has significantly impaired hepatic function at the screening visit (Part A Visit 1) or prior to dosing, defined as any of the following:
  - ALT or AST  $> 5 \times$  ULN
  - TBL (serum total bilirubin)  $> 1.5 \times$  ULN or INR  $> 1.5$ . Note that for participants diagnosed with Gilbert's disease, TBL  $> 3.0 \times$  ULN and/or direct bilirubin  $> 1 \times$  ULN are exclusionary.
  - Serum ALT or AST  $\geq 3 \times$  ULN with the presence of fatigue, nausea, vomiting, right upper quadrant pain or tenderness, fever, rash, and/or eosinophilia ( $> 5\%$ ).
  - Elevated ALT or AST at screening (Part A Visit 1), should be discussed with the medical monitor prior to randomization (Part A Visit 3); the medical monitor may allow for a confirmatory re-draw prior to randomization.

*This criterion can only be confirmed once the laboratory results are available.*

26. Has clinically significant impaired renal function at screening (Part A Visit 1), as evidenced by an estimated glomerular filtration rate (Schwartz equation)  $< 60$  mL/min.

27. Is a female participant of CBP, who is pregnant (positive pregnancy test), lactating or planning pregnancy during the course of the study and for 3 months thereafter.
28. Participant has any known or suspected history of alcohol or substance use disorder.

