## 10.6. Appendix 6: Liver Safety: Actions and Follow-up Assessments

All investigational sites are required to submit to the sponsor PVD the laboratory results for any participant after randomization that meets the criteria for the selected laboratory parameters as follows:

- Serum ALT or AST  $> 3 \times \text{ULN}$  with the presence of fatigue, nausea, vomiting, right upper quadrant pain or tenderness, fever, rash, and/or eosinophilia ( $> 5\%$ ).
- ALT or AST  $> 8 \times \text{ULN}$ .
- ALT or AST  $> 5 \times \text{ULN}$  for  $> 2$  weeks.
- ALT or AST  $> 3 \times \text{ULN}$  **and** (TBL  $> 2 \times \text{ULN}$  **or** INR  $> 1.5$ ).

These reports must be sent to the sponsor PVD using the fax number or by e-mail for SAE reporting within 24 hours of becoming aware of the results. In addition, please send a copy of the participant's baseline laboratory results with all reports to the sponsor PVD.

Abnormal values in AST and/or ALT with or without concurrent abnormal elevations in TBL that meet the criteria outlined above are considered potential cases of drug-induced liver injury and will be considered as protocol-defined criteria for withdrawal and important medical events. The investigator will arrange as soon as possible (within 24 hours of notice of abnormal results) for repeat assessment of ALT, AST, TBL, INR, full blood count (and differential count), eosinophil counts, ALP, and GGT levels, creatine kinase levels, detailed history, and physical examination. Participants should be followed with frequent (every 48 to 72 hours) repeat clinical laboratory assessments and any other appropriate assessments until all abnormalities have normalized (in the investigator's opinion) or returned to the baseline state.

Elevations in ALT or AST  $> 3 \times \text{ULN}$  **or** TBL  $> 2 \times \text{ULN}$  alone are not considered potential cases of drug-induced liver injury, but will be followed as detailed above, within 72 hours' notice of abnormal results. If the participant is no longer at the investigational site, repeat assessments may be performed at a local laboratory and the results sent to the sponsor PVD.

Refer to [Section 7](#) for study withdrawal/discontinuation criteria.

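### Section 9.4.5.3 plans no participant count by multiple of ULN, so ALT/AST rises from a raised baseline or found off schedule, and below the Appendix 6 criteria, are counted only if reported as AEs

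*Combined protocol and SAP*

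**What the plan says.** Section 9.4.5.3 gives the stated laboratory analysis. First: "Clinical laboratory data at each visit, along with the change from baseline and percent change from baseline to each post-baseline visit will be summarized". Second: "Categorical shift tables will also be presented, showing the numbers of participants with values outside the normal range". Section 9.4.1 sets the default statistics for continuous data, which include the minimum and maximum.

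Elsewhere the protocol treats the liver as a known target. Section 2.3 lists transaminase elevations among the most common side effects and adds: "Serious side effects include hepatocellular injury, somnolence and sedation, suicidal behavior and ideation". Laboratory tests are a secondary safety endpoint in Part A and a primary endpoint in Part B (Section 3).

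The protocol acts on liver results in multiples of ULN. Section 7.1 and Appendix 6 (Section 10.6) share four criteria:
- ALT or AST >3 × ULN with listed signs, symptoms or eosinophilia
- ALT or AST >8 × ULN
- ALT or AST >5 × ULN for >2 weeks
- ALT or AST >3 × ULN with TBL >2 × ULN or INR >1.5

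Of ALT or AST >3 × ULN alone, or TBL >2 × ULN alone, Appendix 6 says that these "are not considered potential cases of drug-induced liver injury, but will be followed as detailed above".

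Entry criterion 25 (Section 5.2) excludes ALT or AST only above 5 × ULN, or at or above 3 × ULN with the listed signs. Criterion 49 repeats this for Part B.

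**The concern.** A shift table against the normal range records one fact per child: whether the value moved across a limit of that range. A child who enters above the limit cannot move up across it, however far the value rises. A child who goes from 0.9 to 1.1 × ULN counts the same as one who goes from 0.6 to 4 × ULN.

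Section 9.4.5.3 also gives no rule for samples taken between visits, and that is where much of the liver follow-up falls. Appendix 6 asks for repeats every 48 to 72 hours and applies the same follow-up to isolated elevations. Section 4.1 asks for liver tests within a month of relevant dose or medication changes after Part B Week 14. Central testing is preferred there, but "if done locally, laboratory results should be filed in source documents", with clinically significant abnormal results recorded as AEs.

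At stake is whether the report can say, from laboratory data and by arm, how many children crossed each threshold the protocol itself uses. Without that, the count of moderate elevations depends on investigator judgement.

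**Working it through.** The plan states no rate or figure for liver tests, so there is none to reproduce. The check sets the sections side by side, with illustrations. Values in × ULN are assumed; 60 per arm is the maximum in Section 4.4.

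**1. Which elevations have a route into a participant count?**

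| ALT/AST result | Appendix 6 criterion met? | Where counted by participant |
|---|---|---|
| >3 × ULN with listed signs, or with TBL >2 × ULN or INR >1.5 | yes | AE, special-interest and discontinuation summaries |
| >8 × ULN | yes | same |
| >5 to 8 × ULN for >2 weeks | yes | same |
| >5 to 8 × ULN for up to 2 weeks, none of the above | no | shift table if from a normal baseline at a tabulated visit; otherwise only if reported as an AE |
| >3 to 5 × ULN, any duration, none of the above | no | same as the row above |

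The last two rows are the residual gap. The two-week limit applies only above 5 × ULN.

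**2. What do the planned tables show for a rise from a raised baseline?** Let k of 60 children go from 1.5 to 7 × ULN at a visit while the rest stay at 0.6.
- Change per child: 7 − 1.5 = 5.5 × ULN, or 5.5/1.5 = +367%.
- Mean change: k × 5.5/60.

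| k | Normal-to-high shifts | Mean change | Median change | Maximum value | Maximum change | Count >3 and >5 × ULN |
|---|---|---|---|---|---|---|
| 1 | 0 | 0.09 | 0 | 7 | 5.5 | 1 |
| 3 | 0 | 0.28 | 0 | 7 | 5.5 | 3 |
| 6 | 0 | 0.55 | 0 | 7 | 5.5 | 6 |

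The maximum reveals the rise but is the same for one child and for six. Only the last column, which is not planned, gives the count.

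From a normal baseline, 3 of 60 going from 0.6 to 4 × ULN move the mean by 3 × 3.4/60 = 0.17 × ULN. They are counted as shifts, but not told apart from marginal ones.

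**3. How many children could this affect?** The documents give no figure for raised baselines. If 5% to 30% enter above ULN (assumption), that is 3 to 18 of 60 per arm.

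**4. Can an episode fall between visits?** Scheduled post-dose biochemistry in Part A is on Days 29, 57 and 99 (Table 1). The gaps are 57 − 29 = 28 and 99 − 57 = 42 days. If the Day 57 test is not required (it is conditional in Section 8.3.4), the gap is 99 − 29 = 70 days. An episode of up to 14 days fits inside any of these. At one repeat every 72 to 48 hours, 14 to 21 samples fit into 42 days and 23 to 35 into 70 days. None has a stated place in Section 9.4.5.3.

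**5. Which baseline?** Section 8.3.4 makes Visit 1 results the Part A laboratory baseline and Part A Visit 9 results the Part B baseline. Section 9.4.1 uses the last value before first dose and, unless stated otherwise, carries it into Part B. Take a child at 0.6 at the Part A baseline, 1.5 at Visit 9 and 7 × ULN in Part B. Under Section 8.3.4 the change is 7 − 1.5 = 5.5 with no shift. Under Section 9.4.1 it is 7 − 0.6 = 6.4 with a normal-to-high shift.

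**The case against.** The strongest objection is that Section 9.4 calls itself a summary and, like Section 9.4.6, defers detail to an SAP. That SAP's safety text is not in the documents reviewed and may already hold such tables. This stands as a limit: if it does, confirmation is enough. But Section 9.4.5.3 is not merely silent. It names a method, and that method is less sensitive than one on the protocol's own scale.

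Several stronger readings are tempting, and the documents do not support them:
- *Laboratory tables are restricted to scheduled visits.* The section says each visit and does not mention unscheduled samples. They have no stated place, but they are not excluded.
- *Serious liver harm would be lost, or results could not be set against the stopping thresholds.* Results meeting the four criteria, at any time after randomization, are potential drug-induced liver injury and require IMP discontinuation. Drug-induced liver injury is an AE of special interest (Section 10.4.3), and Section 9.4.5.2 tabulates those AEs and AEs leading to permanent cessation.
- *A rise to 3 to 8 × ULN is always missed.* From a normal baseline at a tabulated visit it is a shift.
- *The Part B interval from Day 169 to Day 337 (168 days) without scheduled liver tests is an analysis error.* It is a feature of the visit schedule; more tables would add no samples.

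It is also fair that local testing is the exception, that Appendix 6 sends local repeats to the sponsor, and that elevated screening values must be discussed with the medical monitor. These reduce the number of children affected, which remains unknown.

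**Conclusion.** The point holds for a defined band of results. ALT/AST above 3 to 5 × ULN for any duration, or above 5 to 8 × ULN for up to 2 weeks, meets no Appendix 6 criterion when there are no listed signs and no TBL or INR criterion is met. If it starts from a raised baseline or is found off schedule, it is counted by participant only when the investigator reports an AE.

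The maximum shows the largest rise at a visit but not how many children had one: 0 shifts and the same maximum whether 1, 3 or 6 of 60 are affected. The number of children exposed to this blind spot rests on the assumed 5% to 30% raised at baseline. The verdict also assumes that the separate SAP does not already contain the counts.

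This is a worthwhile, inexpensive improvement to the reporting of a named toxicity. It is not a failure to capture serious liver injury.

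**What to change.** Add to Section 9.4.5.3, or confirm in the SAP, for Part A by arm and for Part B:
- the number and percent of participants whose worst post-baseline ALT or AST, over all available scheduled and unscheduled results, is >3, >5 and >8 × ULN, split by baseline at or below ULN and above ULN (the split separates new elevations from ones already present);
- the number with ALT or AST >3 × ULN together with TBL >2 × ULN or INR >1.5.

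Include local values where they are available to the sponsor. Reconcile the laboratory baseline definitions in Sections 8.3.4 and 9.4.1 for both parts, because the choice can alter the shift and change results. A split by concurrent valproic acid, which Section 8.3.4 names as a risk factor, is optional.

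The cost is two or three descriptive tables and the matching SAP wording. Testing, dosing and stopping rules do not change.
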